Randomization. Following baseline testing, patient participants will be randomized into TangiblePBCM ($n = 70$) and VoucherPBCM ($n = 70$) conditions. We will stratify on one or more of the following variables: age, involvement in medication-assisted treatment for opioid use disorder (yes/no), working memory score from modified Brown-Peterson test ($<$ or \geq Veteran-specific norm), and current diagnosis of bipolar or psychotic illness (yes/no). A minimization approach may additionally be employed in order to allow for stratification on an expanded set of potentially-relevant clinical and demographic factors. Working memory ability was identified as a potential focus of stratification because it is expected to relate to other FMDM constructs of interest and Veteran-specific norms are available for the modified Brown-Peterson test [67]. Participants will be informed of PBCM treatment assignment during scheduling of the initial CM treatment appointment. Participants previously assigned to a TAU only condition will continue to be followed for check-in and follow-up procedures if agreeable to doing so. To maximize options for future data analysis, this may apply to individuals previously assigned to TAU who elect to begin standard PBCM through CTAD rather than continuing in the TAU only treatment condition as part of the study.

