Treatment. All participants will receive treatment-as-usual during the 12-week treatment interval, which will entail recommended participation in at least two outpatient group and/or individual psychotherapy encounters through CTAD per week; participants will additionally continue pharmacotherapy for substance use and/or other mental health conditions, if applicable. For participants assigned to either Prize-based Contingency Management (PBCM) condition, PBCM will be used and implemented in accordance with the VA protocol for CM, as well as guidance on PBCM, more generally. PBCM involves one-on-one sessions with a provider, during which a urine specimen provided by the patient is tested for cocaine using a point-of-care dip-test. Results of point-of-care testing are then shared with the patient and negative results are reinforced with draws from a fish bowl containing 500 paper slips, 250 of which award small, large, or jumbo prizes (remaining slips deliver words of encouragement). Patients are reinforced with a single prize draw for their first negative specimen; an additional prize draw is added for each consecutive negative result (up to 8 prize draws per session). Abstinence-contingent prize draws are reset to one upon either a positive test result or missed appointment. The proposed work will systematically evaluate two variants of PBCM used within the VA (detailed below) which will be administered twice weekly during 15-20 minute sessions over a 12 week period. The probability of each reward magnitude will be the same in both treatment conditions. Specifically, 41.8% of paper slips will award a small prize, 8% will award a large prize, and 0.2% will award a jumbo prize. During the active treatment period, CM treatment data (i.e., attendance, urinalysis results, prize outcomes) will be logged by the CM provider, and may also be followed through chart review. Participants will additionally be asked to provide regular updates regarding any changes in their housing status or medications (including changes in dosing schedule and/or clinic privileges for patients in medication-assisted treatment) and participation in non-VA substance use treatment (e.g., 12-step meetings in the community). Under unusual circumstances in which a Veteran's prolonged absence from in-person treatment is unavoidable (e.g., due to illness or travel) one or more CM sessions may be conducted via VVC using oral fluid testing (i.e., methods already reviewed and approved under Substudy 1).

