Chart Abstraction Procedures: Information in participant electronic health records will be reviewed and data from CPRS may be added to study records at several points during the study. Prior to providing written informed consent, prospective participants undergoing telephone screening will be asked to verbally consent to review of their CPRS records by study personnel. During screening procedures (and following either verbal (by phone) or written (in person) consent), information relevant to participant eligibility will be reviewed and documented. Eligible participants who enroll in the study will also be subject to additional chart abstraction procedures throughout the course of the study. Chart abstraction will generally occur on an approximately weekly basis during the 12 week treatment interval and will primarily involve documentation of outpatient substance use/behavioral health treatment engagement, missed and cancelled substance use/behavioral health appointments, missed doses of medication-assisted treatment (if applicable), lab-based drug-alcohol urinalysis results, changes in medications, changes to housing or legal status, and/or any other relevant changes to psychiatric or medical status. Data from Contingency Management sessions may also be reviewed for consistency with study tracking logs. In addition, data on previous courses of Contingency Management participants may additionally be abstracted for those with prior Contingency Management treatment experience. Following the 12 week treatment interval, chart abstraction procedures will continue for participants assigned to one of the two Contingency Management treatment conditions but will occur on an approximately monthly basis. Examples of forms used for Chart Abstraction thought the Dacima Clinical Suite are included under Section 15 (Miscellaneous Documents). Following consent to the study, data on engagement with CM treatment, not delivered through the study, may also be derived from review of the patient's chart.

Use of Meal Tickets: Participants will be eligible to receive a same-day meal ticket if scheduled for >3 hours of testing during any given visit. In order to ensure comparable prize options for participants assigned to VoucherPBCM and TangiblePBCM, a meal ticket option will also be made available in the CM Prize Cabinet.

Use of Bus Tickets: Need-based travel assistance will be made available to all participants in the form of single use bus tickets.

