Power Analysis and Sample Size. In analyses of baseline predictors of treatment response in CM recipients (estimated $n = 119$ -140) and long-term (i.e., six month) outcomes (estimated $n = 105$ -140), using the statistical rule of thumb of needing 10 observation per predictor, our originally projected sample size would provide adequate power to include 10-14 variables in regression-based analyses. Random Forest methods are further supported for an expanded set of variables, as this highly flexible and powerful approach has been validated in “wide datasets,” wherein the number of predictors exceeds the number of observations. With the anticipated enrollment of 140 participants, there will additionally be adequate power ($\beta = 0.20$, alpha = 0.05) to detect an effect size of $f = 0.12$ for the treatment adherence (adherent, non-adherent) X time (baseline, follow-up) interaction, supporting planned comparison of treatment-related change in neural and cognitive-behavioral measures between PBCM adherent and non-adherent Veterans. Assuming 15% attrition, the estimate of the detectable effect size for the treatment X time interaction for a total sample size of 119 is $f = 0.13$. The anticipated effect size of treatment-related change in synchronization likelihood between ACC-IPFC electrode sites is not known. However, previous work has established a medium-to-large effect size for treatment-related change in the ERN and N2 (in association with cognitive training).[74,75]

It was necessary to revise our original analytic plan to accommodate a smaller sample size than that originally projected. Recruitment under the current protocol was initially delayed due to institutional barriers that prevented timely acquisition of our EEG system. While recruitment was promptly initiated after our equipment was finally received, approximately three months later, all research activities were suspended due to risks posed by the COVID-19 pandemic. Due to the collection of EEG data and the nature of the interventions under study (e.g., need to be in the physical presence of the prize cabinet to potentially benefit from the increased psychological proximity of reward), it was not possible to convert the current protocol to be conducted fully remotely during the pandemic. A series of administrative

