Specific Aim 2. Evaluate longitudinal change in cognitive-behavioral and EEG-based indices of FMDM during CM. Engagement in PBCM will be associated with differential enhancement of control-related theta synchronization between ACC and IPFC during high conflict events in the Parametric Conflict Flankers task, relative to PBCM nonadherence and will also foster greater improvement in working memory and episodic future thinking effects on delay discounting (Hypothesis 2a). Individual differences in treatment response trajectory during CM will also be explored as a factor in neuroadaptive change during treatment (Exploratory Sub-Aim).

Increased functional connectivity within control-related brain networks in conjunction with CM would reflect important mechanisms of neural recovery facilitated by this intervention. I will receive training in functional connectivity analysis of EEG data, which may include a series of learning experiences guided by my co-mentor, [name], and consultants, Drs. [name], [name], and [name]. Most importantly, I will receive training in synchronization likelihood, a nonlinear approach to estimating functional connectivity which measures statistical dependencies in dynamic time series and can thus characterize both linear and nonlinear interdependencies in EEG data. This technique may be applied to evaluate synchronization strength between pairs of electrodes and within frequency bands, based on a priori hypotheses, although more traditional functional connectivity measures may also be utilized. Specifically, theta frequency synchronization between ACC and IPFC electrode sites will be computed to quantify transient network dynamics related to control modulation. Treatment-related change in

executive working memory and delay discounting behavior will also be evaluated as cognitive-behavioral indicators of FMDM-related function.

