Repeated measures analysis of covariance (ANCOVA) will be conducted to evaluate treatment-related change in the following indices of FMDM between PBCM adherent and non-adherent: (1) control-related theta synchrony between ACC and IPFC, (2) Brown-Peterson working memory score, and (3) change in the episodic future thinking effect in delay discounting slopes ($\Delta \ln(k)$). A general linear model design will be utilized including assessment latency (baseline versus follow-up) as a within-subjects factor. In order to account for differences in substance use, adherence, and PBCM treatment condition, these factors (% days of use, % sessions attended, PBCM condition) may also be considered as covariates or between-subjects factors using a median split approach. Tukey's HSD (or equivalent) will be used for post hoc evaluation of marginal means to clarify main and interaction effects. Adjusted marginal means may be used to investigate covariates as moderators of the treatment-by-time interaction. Given the previously identified relationship between ACC-IPFC theta phase synchrony and amplitude of the ERN and conflict N2,66,67 treatment-related change in these ERPs may also be evaluated using the same approach. Correlations between ERN/N2 amplitudes and ACC-IPFC theta synchrony, as well between EEG and cognitive-behavioral measures, may also be computed for each timepoint to identify significant linear relationships between dependent measures. To account for the constraints of a reduced sample size, we may employ alternative statistical approaches as needed—particularly to address non-normality and other assumption violations that could compromise model validity.

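### Aim 2 attributes neurocognitive change to PBCM from a self-selected adherence contrast that it cannot separate from usual-care dose or general engagement

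*Combined protocol and SAP*

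**What the plan says.** All references are to the combined protocol and SAP.

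- **Treatment received.** The design description states that both CM groups get PBCM on top of TAU. Section 4 (Treatment) defines TAU as "recommended participation in at least two outpatient group and/or individual psychotherapy encounters through CTAD per week". That is a recommendation, so the amount attended can vary.
- **Comparators.** Section 4 (Randomization) allocates patients to two PBCM variants only. It adds that "Participants previously assigned to a TAU only condition will continue to be followed for check-in and follow-up procedures", if they agree, and that this may include people who go on to start standard PBCM in the clinic. They have no stated role in Aim 2. The sample size justification in Section 6 reports that a sufficient healthy comparison sample could not be enrolled.
- **Analysis.** Section 4.1 (Specific Aim 2) plans a repeated measures ANCOVA of change in theta synchrony, working memory score and the delay discounting effect, PBCM-adherent against non-adherent. The optional covariates or split factors are (% "days of use, % sessions attended, PBCM condition"). The revised Aim 2 sample size text names only adherence and abstinence.
- **Data available.** Section 4 (Chart Abstraction Procedures) provides for roughly weekly "documentation of outpatient substance use/behavioral health treatment engagement" during treatment, including missed appointments. The Aim 2 missing-data paragraph says treatment engagement will come from chart review and lists it with the covariates of interest.
- **Planned reading.** Specific Aim 2 says increased connectivity "would reflect important mechanisms of neural recovery facilitated by this intervention" and that PBCM engagement will foster gains in working memory and delay discounting. The abstract in Section 2 looks for enhancement of function through PBCM.

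**The concern.** A patient who keeps CM appointments is likely to keep other appointments in the same clinic. CM adherence may then stand in for total treatment received, or for motivation. A positive adherence-by-time result would fit a PBCM mechanism, a TAU dose effect, or neither.

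The plan's own background makes TAU a credible rival explanation. Section 2 notes that more than half of CM responders may do as well in TAU, and that recent work in Veterans did not show a significant CM effect over TAU.

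Aim 2 exists to clarify how CM works. The significance text in Section 2 suggests that the mechanisms found may later be targeted by cognitive training, neurofeedback or stimulation. A misattributed result could send that work after the wrong ingredient.

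**Working it through.** **1. The plan's power figures.** They are checked first to show that they are not the problem. The text starts "With the anticipated enrollment of 140 participants" and gives 80% power at alpha 0.05 for f = 0.12, then f = 0.13 at N = 119. For a 2 × 2 within-between interaction, λ = N·m·f²/(1−ρ), with m = 2 and df = 1 and N−2. The pre-post correlation ρ is not stated; 0.5 is assumed.

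- N = 140: λ = 140·2·0.12²/0.5 = 8.06, power 80.5%.
- N = 119: λ = 119·2·0.13²/0.5 = 8.04, power 80.3%.
- N = 36: detectable f is 0.304, 0.240 and 0.170 at ρ = 0.2, 0.5 and 0.75. This covers the stated 0.17 to 0.30.

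The figures reproduce. Power does not bear on attribution.

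**2. Effect of omitting TAU attendance.** Let r be the correlation of CM adherence with TAU attendance, and q that of TAU attendance with change. Neither is in the documents; both are assumed. With no PBCM effect, adherence and change still correlate at r·q. By Fisher's z at N = 36, the shift is atanh(r·q)·√33. For r = 0.6 and q = 0.4, r·q = 0.24 and the shift is 0.2448 × 5.745 = 1.406. The rejection probability is then P(Z > 0.554) + P(Z < −3.366) = 29%. Simulation agrees:

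| r | q | r·q | Fisher z | Simulated, continuous adherence | Simulated, median split |
|---|---|---|---|---|---|
| 0.3 | 0.2 | 0.06 | 6.4% | 6.8% | 6.0% |
| 0.4 | 0.3 | 0.12 | 10.7% | 10.4–11.5% | 9% |
| 0.5 | 0.4 | 0.20 | 21.4% | 21.8% | 15.4% |
| 0.6 | 0.4 | 0.24 | 29.0% | 30.0–30.4% | 20% |
| 0.7 | 0.5 | 0.35 | 55.5% | 55.6–57.4% | 37–39% |

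The simulation leaves out the plan's optional covariates for days of use and PBCM condition.

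**3. Effect of adding TAU attendance.** In this set-up rejection returns to about 5% in every cell. That is built in, because TAU is the only confounder simulated. Suppose instead that unmeasured motivation drives CM attendance, TAU attendance and change, with assumed loadings 0.6, 0.6 and 0.4. The CM–TAU correlation is 0.36, and each correlates 0.24 with change. The partial correlation of CM attendance with change is (0.24 − 0.36·0.24)/√[(1−0.36²)(1−0.24²)] = 0.170. The adjusted test then rejects about 16% of the time. Loadings of 0.4, 0.4, 0.3 and 0.7, 0.7, 0.5 give about 9% and 25%.

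**4. Cost in precision.** Variance inflation is 1/(1−r²): 1.19, 1.56 and 1.96 for r = 0.4, 0.6 and 0.7. At N = 36, ρ = 0.5 and f = 0.24, power falls from 80% to 73%, 61% and 51%, before any gain from variance that TAU explains.

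**The case against.** Three replies have weight.

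*The plan already covers TAU engagement.* A reader might infer that TAU attendance is simply absent. That goes too far. The missing-data paragraph lists chart-derived treatment engagement with the covariates of interest, and the design description uses nearly the same words for outpatient engagement. The model paragraph also does not say whether the sessions attended are CM sessions, although Specific Aim 1 uses the CM label and adherence is the stated purpose. What stands is that no model term for TAU attendance is defined and the two paragraphs do not match.

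*The hypothesis is associational.* The connectivity hypothesis is worded as an association relative to non-adherence. The abstract states an aim, not a finding, and the follow-on work is only a possibility. This is fair, but the same hypothesis sentence goes on to say foster, and the next paragraph credits the intervention.

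*Adjustment may mislead.* CM may itself raise TAU attendance, in which case adjusting removes part of a real CM effect. This stands, and it limits the remedy to a sensitivity analysis.

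A reader might also infer that an adherence effect surviving TAU adjustment could be called CM-related. The documents do not support that: motivation is unmeasured as a confounder here, and non-VA treatment, which Section 4 tracks, is also outside the model. Nor are the former TAU-only participants a secure CM-free reference. Some may have begun PBCM, follow-up is voluntary, and no count with follow-up EEG is given.

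**Conclusion.** The concern holds as one of attribution. Aim 2 can show that change goes with engagement in PBCM plus TAU. It cannot show that PBCM produced the change, with or without TAU adjustment. No figure in the plan is wrong.

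The size is illustrative only. At N = 36 with no PBCM effect, omitting TAU attendance gives false significance of about 6% to 57% with continuous adherence, and about 6% to 39% with a median split, against a nominal 5%. The range rests on assumed correlations (r from 0.3 to 0.7, q from 0.2 to 0.5). The upper end is the worst corner, and at the mildest setting the distortion is slight.

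**What to change.** 1. In Specific Aim 2, and wherever the abstract's phrasing is carried into conclusions, state the result as change associated with engagement in PBCM plus TAU. Keep this wording whether or not the effect survives adjustment.
2. Reconcile the Aim 2 model and missing-data paragraphs. Define the sessions-attended covariate as CM sessions, and treatment engagement as non-CM outpatient encounters attended per week, from the chart.
3. Report the adherence-by-time estimate without and with that covariate, side by side, as a sensitivity analysis. State that TAU attendance may be a confounder or a mediator, and that motivation and non-VA treatment remain unaddressed. Do not make persistence after adjustment a test for calling the effect CM-related.
4. If former TAU-only participants with follow-up EEG are shown, do so descriptively and only for those who did not start PBCM.

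The cost is wording plus one extra model on data already abstracted. The adjusted estimate will be less precise (variance inflation about 1.2 to 2.0 for CM–TAU correlations of 0.4 to 0.7), so failure to persist should not be read as absence of a CM effect.

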
The proposed work will test key predictions of the FMDM account of CM with implications for (1) improved treatment effectiveness and (2) targeted treatment delivery. Individuals with CUD (n=140) will be recruited upon engagement with outpatient substance use services and assigned to 12 weeks of TangiblePBCM (n=70) or VoucherPBCM (n=70). Participants in all conditions will complete EEG and cognitive-behavioral assessments of core FMDM constructs (i.e., goal-informed cognitive control processes, executive working memory, episodic future thinking, and reward anticipation) before and after the 12 week treatment interval. Self-report measures of other clinically-relevant indicators (e.g., addiction propensity and severity, motivation, self-efficacy) will also be evaluated and outcomes (treatment engagement, subjective and objective measures of substance use) will additionally be

followed throughout the 12 week treatment interval and for 6 months post-treatment in both CM groups. Aims and hypotheses are as follows:

Specific Aim 1: Evaluate the utility of EEG and cognitive-behavioral measures of FMDM as predictors of differential treatment outcomes in TangiblePBCM versus VoucherPBCM.

Hypothesis 1a. FMDM-related measures will predict differential outcomes in TangiblePBCM relative to VoucherPBCM, with more FMDM-impaired individuals demonstrating improved treatment response in the former relative to the latter.

Hypothesis 1b. Inclusion of predictors from the FMDM account will significantly improve performance of predictive models forecasting short- and long-term outcomes in CM and inclusion of these predictors will be robust to model-based constraints favoring variables with lower measurement costs.

Specific Aim 2: Evaluate treatment-related change in EEG and cognitive-behavioral correlates of FMDM-related cognitive functioning during CM.

Hypothesis 2a. Individuals who reliably engage in TangiblePBCM and VoucherPBCM will demonstrate greater treatment-related change in functional connectivity networks underlying goal-informed cognitive control processes, as well as behavioral measures of working memory and future-oriented decision-making, relative to individuals who demonstrate poor PBCM adherence.

Exploratory Sub-Aim. Longitudinal change in FMDM-related measures will be investigated in relation to patterns of abstinence during PBCM and will reflect distinct treatment response trajectories.

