Additional exploratory analyses may also be conducted to investigate trajectories of recovery during PBCM in relation to neuroadaptive change. I will receive specialized training in multilevel modeling approaches to longitudinal data analysis, including use of growth mixture models to resolve latent subgroups exhibiting distinct patterns of longitudinal change. For participants assigned to both PBCM conditions, longest duration of cocaine abstinence may be computed on a weekly basis from within-treatment urinalysis results and attendance (unexcused, missed appointments will also be considered to end a period of abstinence). Growth mixture modeling may subsequently be employed to evaluate intra-individual change in the longest duration of abstinence achieved during PBCM treatment and determine if distinct change profiles meaningfully represent inter-individual variance. If identified, subgroups exhibiting distinct trajectories in PBCM may also exhibit different patterns of neural recovery within functional connectivity networks underlying cognitive control and reward representation. Exploratory, network-based analyses may therefore also be conducted (if applicable) and may generate new insights into neuroadaptive processes that reflect and may also support sustained abstinence in CM. Cocaine users have previously been demonstrated to exhibit reduced interhemispheric functional connectivity within the dorsal frontoparietal control network, which is thought to support goal-directed top-down control of attention and behavior, as well as representation and anticipation of future rewards. My training in functional connectivity analysis of EEG data will support exploratory analysis of network-level disturbances in CUD, as well as potential treatment-related change in interhemispheric functional connectivity within the dorsal frontoparietal control network in relation to CM. Using methods previously described by my consultants, Drs. [name], [name], and [name], I may also employ synchronization likelihood to identify localized functional connectivity networks that significantly differ between CUD subgroups exhibiting different patterns of cocaine abstinence during CM. Briefly, pairwise synchronization likelihood will be computed between all pairs of EEG channels for reward- and control-

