related epochs derived from Incentive Delay and Flankers tasks, respectively. Non-parametric, network-based statistics will subsequently be employed to identify pairings which differ significantly between CUD subgroups at baseline and follow-up, including potential differences in interhemispheric functional connectivity within the dorsal frontoparietal control network. Training offered by my consultants would also afford the opportunity to combine synchronization likelihood with graph theoretic approaches to functional connectivity analysis. Consequently, additional exploratory analyses can target differences in network-level properties within local (e.g., strength, local efficiency, betweenness centrality) and global (e.g., path length, small worldness, global efficiency) functional connectivity structures. However, it is noted that additional exploratory analyses can only be undertaken if the final sample size is sufficient to support them.

Missing Data Strategies: Individuals lost to follow-up will be excluded from these analyses due to necessary inclusion of longitudinal measures from the follow-up timepoint. It is anticipated that covariates of interest will be available for all individuals who complete the follow-up assessment session. Specifically, treatment engagement will be determined on the basis of chart review and self-reported substance use will be evaluated on a weekly basis. For participants who miss one or more check-in assessment during the treatment period, the timeline follow-back procedure will be extended to evaluate the full period between the present and previous study contact. In my previous longitudinal study of substance users, I was able to collect all necessary follow-up data on 80.8% of my originally enrolled sample. However, it is also possible that unexpected circumstances may require imputation of missing data values. In such cases imputation of missing values will leverage available within- and between-subjects data.

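### The optional network analysis is motivated by neural recovery, but its edge-level test compares abstinence subgroups at each visit and specifies no test of change

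*Combined protocol and SAP*

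**What the plan says.** The Exploratory Sub-Aim in section 2 (Study Objectives & Design) asks about change: "Longitudinal change in FMDM-related measures will be investigated in relation to patterns of abstinence during PBCM".

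The exploratory part of Specific Aim 2 in section 4.1 would use growth mixture modelling to look for abstinence-trajectory classes. It then motivates the network work by recovery, since "subgroups exhibiting distinct trajectories in PBCM may also exhibit different patterns of neural recovery within functional connectivity networks". It also names as a target "potential treatment-related change in interhemispheric functional connectivity within the dorsal frontoparietal control network in relation to CM". The groups to be compared are "CUD subgroups exhibiting different patterns of cocaine abstinence during CM", so they are formed from observed response and not by randomisation.

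The test follows a short summary of how pairwise synchronization likelihood is computed over all channel pairs: "Non-parametric, network-based statistics will subsequently be employed to identify pairings which differ significantly between CUD subgroups at baseline and follow-up". The interhemispheric question is folded into that same between-subgroup comparison.

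A time factor does appear earlier in Aim 2, in the repeated-measures ANCOVA: "A general linear model design will be utilized including assessment latency (baseline versus follow-up) as a within-subjects factor". That model covers ACC-lPFC theta synchrony, the Brown-Peterson score and Δln(k), with ERN and N2 optional. It does not cover the channel-pair networks. The section closes by making the additional exploratory analyses conditional on an adequate final sample.

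**The concern.** Whether subgroups differ in recovery is a subgroup-by-time question. A contrast of subgroups at one visit estimates a difference in level. Two such contrasts, one per visit, do not together test whether the difference changed: an edge that is significant at follow-up and not at baseline need not have changed significantly.

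A trait-like difference that is present throughout, and unaffected by treatment, can therefore cross the threshold at follow-up only, by sampling variation. Nothing in the plan stops such an edge from being described as recovery, and recovery is the stated reason for looking. The background section says that neural adaptation found in this study could be targeted by cognitive training, neurofeedback or brain stimulation in later research, so a misattributed edge could misdirect that work.

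**Working it through.** **1. The plan's nearest figure.** No figure is given for the network test. For the adherence-by-time interaction, section 4.1 states detectable f = 0.12 at N = 140 and f = 0.13 at N = 119 (alpha 0.05, power 0.80). For a two-group, two-visit interaction, λ = f²·N·2/(1 − ρ), with 1 and N − 2 degrees of freedom. The pre-post correlation ρ is not stated; ρ = 0.5 reproduces both figures.
- N = 140: λ = 0.0144 × 140 × 2 / 0.5 = 8.06, power 0.805.
- N = 119: λ = 0.0169 × 119 × 2 / 0.5 = 8.04, power 0.803.

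For the revised N = 36, the plan gives f = 0.17 to 0.30. If the same formula and power are meant, this corresponds to ρ from about 0.75 down to about 0.22. The plan's interaction figures thus concern a test of change, which the edge-level test is not.

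**2. What each test responds to.** Suppose one edge has a constant standardised subgroup difference d at both visits and neither subgroup changes.
- Single-visit t test: noncentrality = d·√(n₁n₂/(n₁+n₂)). At 18 v 18 this is d·√(324/36) = 3d. For d = 0.66 it is 1.98, and the test is significant at each visit in about 48% of trials.
- Test on follow-up minus baseline: the constant d cancels, so noncentrality is 0 and the rejection rate is 5% for any d or ρ.

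**3. How often the visits disagree.** The inputs are assumptions: 18 v 18 (an even split of the 36 participants with pre and post data in section 4.1), normal data, two-sided uncorrected 0.05 tests, 40,000 to 60,000 simulated trials per row, and no true change.

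| d | ρ | Significant at follow-up | At both visits | At follow-up only | Change-score test |
|---|---|---|---|---|---|
| 0 | 0.5 | 5.1% | 0.9% | 4.1% | 5.0% |
| 0 | 0.75 | 5.0% | 1.8% | 3.2% | 5.1% |
| 0.4 | 0.5 | 21.6% | 9.4% | 12.2% | 5.0% |
| 0.4 | 0.75 | 21.7% | 13.2% | 8.6% | 4.9% |
| 0.5 | 0.5 | 30.7% | 16.1% | 14.6% | 5.0% |
| 0.5 | 0.75 | 30.7% | 20.6% | 10.1% | 5.0% |
| 0.66 | 0.5 | 48.6% | 31.6% | 17.0% | 5.1% |
| 0.66 | 0.75 | 48.3% | 36.8% | 11.5% | 5.0% |
| 0.8 | 0.5 | 64.6% | 48.9% | 15.7% | 5.1% |
| 0.8 | 0.75 | 64.5% | 53.6% | 10.9% | 5.1% |

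Independent repeats differ by less than one percentage point. With no true difference (d = 0), follow-up only occurs in 3% to 4%, so the excess comes from stable differences.

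**4. Sensitivity.** A 12 v 24 split is similar (d = 0.8, ρ = 0.5: follow-up only 16.3%). At 59 v 60 the size depends strongly on d: with ρ = 0.5 it is 15.9% at d = 0.3 and 0.8% at d = 0.8, because a large stable difference is then nearly always seen at both visits.

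**The case against.** The strongest reply is that little depends on this analysis. It is optional, depends on classes being identified, and runs only if the sample allows. No hypothesis rests on it. That stands, and it sets the severity.

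The plan also never says that a follow-up-only edge will be called recovery, and describing group differences at each visit is legitimate. The text is a summary of methods published elsewhere by consultants, so a joint test may be intended. Aim 2 excludes people lost to follow-up, which a baseline-only contrast would not require. These points are fair. They make the gap one of specification: no joint or change test is written, and one sentence would settle it.

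Three stronger readings are tempting, and the documents do not support them.
- *The plan cannot answer the exploratory sub-aim.* The sub-aim covers FMDM-related measures in general. The Aim 2 sample-size text treats abstinence as a potential covariate, with a median split as an alternative. The repeated-measures model may take percentage of days of use as a covariate or between-subjects factor. One of its outcomes, theta synchrony, is itself a connectivity measure. A change-by-abstinence route exists, though it is optional.
- *Stable edge differences are likely because Aim 1 expects baseline EEG to predict response.* Hypothesis 1a is an interaction with PBCM condition, and Table 1 expects opposite advantages by level of impairment. The trajectory subgroups pool both conditions, so such effects may partly cancel. The Aim 1 EEG predictors are alpha suppression, ERN and N2, not pairwise synchronization. Stable edge differences are possible; the documents do not make them likely.
- *The simulated rates are the error rates of the planned test.* They concern one uncorrected edge, whereas the plan uses network-based statistics over all pairs. A stable edge of 0.66 SD is also significant at both visits about two to three times as often as at follow-up only (31.6/17.0 = 1.9; 36.8/11.5 = 3.2), and that pattern would reveal stability.

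**Conclusion.** The point holds for the optional network analysis only. Its rationale is recovery and treatment-related change, and its one stated edge-level test contains no test of change. That test alone therefore cannot show that abstinence subgroups differ in recovery, and a constant difference could surface at follow-up only. The illustrative size is about 8% to 17% per edge, against about 5% for a change-score test. The assumed difference, retest correlation, even two-group split and absence of network-level correction come from no document, so the figures show direction and rough size only. Hypothesis 2a, and the parts of the sub-aim served by the repeated-measures model, are not affected. Severity: minor.

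**What to change.** In the network paragraph of Specific Aim 2 (section 4.1), state that the network-based statistic is applied to each participant's follow-up-minus-baseline connectivity matrix, permuting subgroup labels. Use a t contrast for two subgroups and an F contrast if growth mixture modelling yields more, since the number of classes is not fixed. Keep the single-visit contrasts as descriptive, with no recovery claim drawn from them. Because the subgroups are formed from observed abstinence, a difference in change remains an association.

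**Cost.** One or two sentences and a different input matrix. No new data are needed: Aim 2 is already limited to participants with follow-up, and usable EEG at both visits is required for any statement about change.

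**Downside.** The variance of a change score is 2(1 − ρ)σ², against σ² at a single visit. The change contrast is therefore less precise when ρ is below 0.5 (SD ratio √(2 × 0.78) = 1.25 at ρ = 0.22) and more precise above it (√(2 × 0.25) = 0.71 at ρ = 0.75). If edge-level retest correlation proves low, that should be reported with the result.
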